Protocol: Peripheral Nerve Stimulation for Shoulder Pain: Dose Response

ID: IRB16-00510

NCT02928055

Document Date: 12/18/2020

8.0 Methods and Procedures I:

8.1 Will this research involve the following Social-Behavioral Procedures:

Check all that apply.

Name _____
 Psychological Testing _____
 Surveys/Questionnaires _____

8.2 Will this research involved any of the following Medical Procedures/Considerations:

Check all that apply.

Name _____
 Collection of Biohazardous Substances _____
 Study of Human Biological Materials (i.e. Urine Collection) _____
 Investigation/Approved Devices _____
 Study of Existing Data _____
 Medical Tests, Comparisons, Evaluations _____
 Clinical Assessments (EEG, EKG, SCID, etc.) _____
 Venipuncture (Blood Draw) _____
 Use of investigational devices _____
 Psychological testing _____

8.3 Identify Data Collection types for this study:

Check all that apply.

Name _____
 Audio-Recording/Video-Recording/Photographs _____
 Chart Review - Prospective _____
 Existing/Retrospective Data/Specimens _____
 Interviews, questionnaires or psychological tests _____

Note if you are doing, recordings, Video-Recording/Photographs then subjects will need to sign the MetroHealth Audio-Video Consent form. See the IRB Forms and Templates.

View: 08-01 Methods and Procedures II

8.1 Methods and Procedures II:

8.4 * Please specify in detail the methods and procedures that are involved in this research:

If this field is not completed your protocol will not be reviewed. Do not enter N/A. Please describe what methods and procedures will be involved in this research.

Study Summary: This is a pilot RCT to explore the role of muscle contraction as a mechanism produced by peripheral nerve stimulation (PNS) to reduce hemiplegic shoulder pain (HSP). Thirty subjects will enroll and receive a 3-week course of percutaneous IM PNS at one of 3 doses. Subjects will be randomized to receive the standard IM PNS treatment (15,120 total contractions), IM PNS at half the standard dose (7,560 total contractions), or IM PNS at 1.5 times the standard dose (22,680 total contractions). Dose will be controlled by differing the stimulation time per day (3h, 6h, or 9h) while keeping constant the duty cycle of stimulation. Subjects will be followed for 12 weeks after treatment.

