PNS Treatment Protocol: After one week for lead stabilization [80], the Sprint PNS System will be programmed for stimulation. Based on over 30-yrs of experience, the Cleveland FES Center established parameters for safe and effective delivery of PNS (pulse frequency = 12 Hz; pulse amplitude = 20 mA; pulse duration = 5-200 usec (set by clinician); duty cycle = 5-sec ramp-up, 10-sec plateau, 5-sec ramp down, 10 sec off; daily stim time (randomized) = 3, 6, 9 hrs/day; total contraction dose (randomized) = 7560, 15120, 22680 contractions). [81] These parameters provide strong fused comfortable muscle contraction with minimal fatigue. [6-12, 49, 62, 71,82-84] Stimulation frequency and amplitude are fixed. The pulse duration is set to produce strong, comfortable contraction of both the middle and posterior deltoids. A balanced biphasic waveform allows an equal amount of current to flow in either phase, creating a safe net zero charge. [85] In this dose-response study, participants receive 3h, 6h, or 9h of stimulation each day. The stimulator keeps an electronic log for compliance monitoring.

Electrode and Electrode Site Surveillance and Electrode Removal: All caregivers and participants will be trained in the assessment of electrode site and the daily placement of the Sprint Pad. The caregiver conducts daily inspections to detect complications. The nurse coordinator inspects the site for infection and performs motor/sensory threshold testing for lead migration and lead integrity, respectively, at the following times: within 48-72 hrs of lead placement, at the beginning of PNS treatment, and at the end of treatment. Inspection and testing of motor/sensory thresholds and impedance may also occur anytime during the 3-wk PNS treatment period as deemed necessary. At the end of treatment, the electrode is removed by gently pulling on the external portion. All participants undergo radiographic surveillance for retained electrode fragments.

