8.5 Does this study only involve the use of existing/retrospective data/specimens?

Check yes or no.

No

8.6 Describe in detail the study design also known as the experimental flow. Include all study procedures a subject will go through, in order of sequence and timing, including frequency of visits, duration of visits, length of subject participation etc. Please Note this needs to be written for an educated person who is not an expert in the field, do not exceed 300 words:

This is also known as NIH Experimental Procedure section or Clinical Trial Procedure/Experimental Flow section. Do not just attach documents in response to this question you must do a study design summary for IRB Review.

The duration of each subject's participation will be ~4 months.

Visit 1 – Consent/Eligibility: Consent form signed; assessed for eligibility per inclusion/exclusion criteria; MMSE administered; BDI, PCS & FABQ administered; medical history, demographics, comorbidities, and medication use recorded; blood drawn for INR (in applicable subjects); pregnancy test (in applicable subjects). (~3.5 hrs)

Visit 2 – Baseline Outcomes Assessment: Study outcome measures (see Outcomes Assessment) administered to establish baseline levels. (~4 hrs)

Visit 3 - Sprint MicroLead (Electrode) Implant Procedure: Testing of muscle response with Sprint Test Needles; Implantation of percutaneous Sprint MicroLead. Subject given instructions on care of Lead exit site. Skin checked, subject queried for medication usage. Randomization to treatment group. Subset of study outcome measures (questionnaires only) administered. (~2.5 hrs)

Visit 4 - 48-72 hour Post-Implant Safety Check: Check the Lead exit site within 48-72 hours of the Implant procedure; dressing changed. (~1 hr)

Visit 5 - Start of Stimulation: Collection of parameter data; programming of external stimulator (Sprint Stimulator). Subject given instructions on use of System and care of Lead exit site. Skin checked, dressing changed, subject queried for medication usage and adverse events. Subset of study outcome measures (BPI-SF only) administered. (~2 hrs)

Phone Call #1 – One week after starting stimulation, subject queried on condition of Lead exit site, pain, adverse events. (30 min)

Phone Call #2 – Two weeks after starting stimulation, subject queried on condition of Lead exit site, pain, adverse events. (30 min)

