There is a rare chance that the Sprint Stimulator may malfunction. It is very unlikely that a stimulator malfunction will be harmful. If there is a problem with the Sprint Stimulator or the Sprint MicroLead, the Stimulator will reset itself such that no stimulation is delivered.

The Sprint Stimulator will not deliver stimulation if it detects a high impedance level indicating a broken lead wire or a faulty lead connection. Subjects will be instructed to contact study staff in the event that an error message is displayed.

9) Risks for pregnant women

The risk of harm to a pregnant woman or fetus is unknown. The device will not be used in any subjects known to be pregnant. If a subject is known to become pregnant during the treatment phase, stimulation will be stopped and the Sprint MicroLead will be removed.

Potential risks of pregnancy will be reduced by administering a pregnancy test in females of reproductive potential at study enrollment. Additionally, the Informed Consent form will advise subjects that the risks of electrical stimulation during pregnancy are unknown and that they should immediately notify the Investigator if they suspect they have become pregnant during the study.

10) Risk of discomfort due to electrical stimulation

Intramuscular electrical stimulation may be perceived by the subject as a tingling or vibrating sensation, which may feel uncomfortable or painful. The risk of discomfort due to stimulation is uncommon. At high stimulation intensities, shoulder pain may worsen.

To minimize the risk of increased shoulder pain as the result of high intensity stimulation, the Investigator will set an appropriate intensity for the stimulation. Should a subject feel pain as the result of stimulation, he or she will be able to turn off the stimulation using the Sprint Stimulator controls. Although muscle fatigue is unlikely with six hours of daily stimulation therapy, subjects may also feel some discomfort if muscle fatigue occurs. If muscle fatigue is observed, the Investigator is able to prescribe several shorter stimulation sessions totaling six hours per day.

Discomfort or pain due to stimulation may occur if the Sprint MicroLead migrates from its original location. Stimulation near the skin surface may be perceived as a "pins and needles" or stinging sensation and may be uncomfortable.

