The 32 subjects randomized to the treatment group each had four percutaneous leads placed that were identical to the Smartpatch Lead. The lead placement procedure was well tolerated. All leads remained intact and free of infection during the 7-week indwelling period. Of the 128 leads placed in this study, the tips of five leads (3.9%) among four subjects (12.5%) broke during removal, none of which resulted in an adverse event. Granuloma formation defined as localized tissue inflammation exhibited by redness, swelling, or pain at the lead exit site was noted for five leads (3.9%) in two subjects (6.3%). All granulomas resolved after lead removal with no further intervention required.

The authors concluded that percutaneous electrical stimulation is safe and effective in reducing post-stroke shoulder pain, with sustained pain reduction in a cohort of subjects to at least 12 months after the end of treatment. Placement of leads in proximity to peripheral nerves within target muscles bypasses cutaneous pain receptors, which minimizes the discomfort of stimulation and ensures stable electrode placement. Further, once placed, skilled personnel are not needed on a daily basis to place electrodes to ensure effective positioning.

In an IRB approved Non Significant Risk (NSR) study, eight chronic stroke

survivors with post-stroke shoulder pain, five with subluxation and three without, received three weeks of peripheral nerve electrical stimulation, 6-hrs daily via a single Smartpatch Lead placed between the motor points of the middle and posterior deltoids, which produced strong contractions of both muscles. The primary outcome measure was pain intensity (BPI 3) on the short form of the BPI. Longitudinal analysis demonstrated that participants experienced significant reduction in pain intensity. Participants also experienced significant reduction in pain interference with daily activities based on BPI 9 ($F=5.9$, $p<0.01$), and significant improvement in QoL based on the bodily pain component of the SF-36 ($F=12.8$, $p<0.001$). All 8 participants exhibited significant pain reduction at EOT. This study indicated that the three-week, single-lead approach produced pain relief comparable to the more complex six week, 4-lead approach. The three participants without subluxation all exhibited substantial pain reduction, which reinforced that pain reduction is not mediated by improvements in subluxation and that subluxation is not a necessary inclusion criterion.

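### The fatigue provision allows split sessions with a fixed six-hour daily total and names no arm, although daily time is randomized to 3, 6 or 9 h

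*Protocol*

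**What the plan says.** Daily stimulation time is the randomized factor. The Study Summary in 8.4 states: "Dose will be controlled by differing the stimulation time per day (3h, 6h, or 9h) while keeping constant the duty cycle of stimulation". The PNS Treatment Protocol in the same section gives "daily stim time (randomized) = 3, 6, 9 hrs/day", with randomized totals of 7,560, 15,120 and 22,680 contractions. It adds: "The stimulator keeps an electronic log for compliance monitoring".

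Muscle fatigue is taken up in 10.5, item 10, on discomfort due to stimulation. One sentence opens "Although muscle fatigue is unlikely with six hours of daily stimulation therapy" and notes that fatigue may still cause some discomfort. The next sentence is the provision: "If muscle fatigue is observed, the Investigator is able to prescribe several shorter stimulation sessions totaling six hours per day". The same text stands in 10.10 (measures to minimize the risks), 18.01 (anticipated adverse events) and 21.24 (complications). It is one sentence in four places, not four rules. No section of the visible text limits it to the 6 h arm or ties it to the assigned dose.

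**The concern.** Splitting a day's stimulation into shorter sessions is a sensible answer to fatigue, because it allows rest while keeping the daily total. The provision keeps the total only for a participant assigned six hours. For a participant assigned nine hours, the total it names is the standard arm's daily dose.

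The trial exists to compare doses. A change of this kind moves delivered dose in the 9 h arm toward the 6 h arm, and does so in the participants who fatigue. Because the protocol would permit the prescription, an investigator could follow the text in good faith and narrow the contrast where nine hours in split sessions might have been tolerable. The stimulator log would record the shorter hours but would not prevent them.

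The likely cause is text not adapted from an earlier regimen. The three-week single-lead study described in 21.21 "received three weeks of peripheral nerve electrical stimulation, 6-hrs daily via a single Smartpatch Lead", and 21.23 still gives a six-hour daily dose alongside the 3, 6 and 9 h statement.

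**Working it through.** **Inputs.** From 8.4: a cycle of 5 s ramp-up, 10 s plateau, 5 s ramp-down and 10 s off; daily time of 3, 6 or 9 h; a three-week course (21 days); 30 participants in three arms. Assumed: equal allocation, so 10 per arm, with 8 to 12 as a range. The day of any switch is also assumed.

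**Reproducing the planned doses.** The cycle lasts 5 + 10 + 5 + 10 = 30 s, so there are 3,600 / 30 = 120 contractions per hour.

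- 3 h: 3 × 120 × 21 = 7,560
- 6 h: 6 × 120 × 21 = 15,120
- 9 h: 9 × 120 × 21 = 22,680

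All three match the protocol. The cycle given in 21.23 (2 + 16 + 2 + 10 s) is also 30 s and gives the same totals. The planned contrasts in mean dose are 22,680 − 15,120 = 7,560 (9 h versus 6 h) and 22,680 − 7,560 = 15,120 (9 h versus 3 h).

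**One 9 h participant moved to six hours a day.** The daily count falls from 9 × 120 = 1,080 to 6 × 120 = 720. The only scheduled contacts between the start and end of stimulation are the two phone calls in 8.6: "One week after starting stimulation, subject queried on condition of Lead exit site, pain, adverse events" and "Two weeks after starting stimulation, subject queried on condition of Lead exit site, pain, adverse events". Fatigue is not a listed query at either call, so day 8 and day 15 are illustrations and not predictions.

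- Switch from day 8: 7 × 1,080 + 14 × 720 = 17,640. Loss 22,680 − 17,640 = 5,040. Kept above standard: 2,520 / 7,560 = 33%.
- Switch from day 15: 14 × 1,080 + 7 × 720 = 20,160. Loss 2,520. Kept above standard: 5,040 / 7,560 = 67%.
- Ceiling, switch from day 1: 21 × 720 = 15,120. Loss 7,560. Nothing kept above standard.

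**Effect of that one participant on the arm mean.** The shift is loss / n, shown as a share of each planned contrast.

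| Switch | n in 9 h arm | Shift in mean | Share of 9 h vs 6 h (7,560) | Share of 9 h vs 3 h (15,120) |
|---|---|---|---|---|
| Day 8 | 10 | 504 | 6.7% | 3.3% |
| Day 8 | 8 / 12 | 630 / 420 | 8.3% / 5.6% | 4.2% / 2.8% |
| Day 15 | 10 | 252 | 3.3% | 1.7% |
| Day 15 | 8 / 12 | 315 / 210 | 4.2% / 2.8% | 2.1% / 1.4% |
| Day 1 (ceiling) | 10 | 756 | 10% | 5% |

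The shift is proportional to the number switched and is zero if none are.

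**The case against.** The strongest reply is that the sentence just before the provision concerns six-hour therapy. Read together, the two may say only that a six-hour day can be split and still total six hours. The provision is permissive, depends on fatigue being observed, and sits in a risk narrative, while the dosing text in 8.4 is explicit for each arm. This stands to the extent that the provision is no instruction to re-dose anyone. It does not remove the point, because on that narrower reading the 9 h arm has no split-session provision at all, although its daily stimulation is 50% longer than the regimen discussed.

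A second reply is that the percentages measure dose reduction in general. A 9 h participant cut to six hours for safety would lose the same contractions under corrected wording. This also stands. The wording itself costs dose only in participants who fatigue and could have managed nine hours in split sessions. The protocol does not say how many that might be, and it describes the parameters as causing little fatigue.

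Third, participants can turn stimulation off if it is painful or stop treatment if it is too uncomfortable, and the treatment forms and clinician manual are attachments not shown. The statement that this is the only response specific to fatigue therefore covers the visible text alone.

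A reader might infer more: that the provision overrides randomization, pulls every arm to six hours, or doubles the dose of a fatigued 3 h participant. The documents do not support this. Assignment is unchanged, the provision obliges nobody, and raising a 3 h participant to six hours because of fatigue is not a plausible use of it.

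**Conclusion.** The point holds in a limited form. As worded, the provision permits a daily total that equals the assigned dose in one arm of three, and it appears to be left over from a single-dose regimen. The practical exposure is the 9 h arm. With 10 per arm assumed, each participant needlessly switched at day 8 or day 15 takes 6.7% or 3.3% off the contrast with the standard arm, or 3.3% or 1.7% off the contrast with the 3 h arm. Those figures rest on assumed switch days and equal allocation. They should not be read as an expected loss, because the frequency of fatigue is not stated. Severity is minor: the wording is wrong for a dose-comparison trial and easy to correct, but it does not undermine the randomized comparison.

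**What to change.** In 10.5, 10.10, 18.01 and 21.24, replace the six-hour total with *the participant's assigned daily time (3, 6 or 9 h)*, and state that a reduction below the assigned time remains allowed when needed for safety. This serves both readings: it keeps the dose where splitting is enough, and it gives the 9 h arm a fatigue provision. Recording such reductions as departures from the assigned dose, using the existing stimulator log, is optional.

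The cost is one phrase and one short clause in a sentence that appears four times, with no new data collection. Aligning the six-hour daily dose in 21.23 would be an editorial tidy-up and is not part of this point.
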